5.2.1 Technical description of mpKnee joint

The knee joint for the Braces used in this study as shown in “Figure 3: Microprocessor controlled knee joint unit” is controlled by microprocessor controlled hydraulics. The knee joint can only dissipate energy and is not capable of energy storage. As the hydraulic unit has two valves, flexion and extension resistance can be controlled independently. This means that flexion resistance can be high but at the same time extension resistance can be low, which is a safety feature.

The unit has a modular design with electronic components connected with the proprietary AXON bus, with the exception of the hydraulic sensor.

The system control is based on signals from several sensors:

- 3D accelerometers and gyroscopes measure motion and orientation in space.
- A hydraulic force sensor measures the load that is transmitted by the Brace system.

ottobock.	CLINICAL INVESTIGATION PLAN	Document number:	PD-PS00120016A-001
		Version number:	7
Project name	Clinical trial comparing C-Brace to KAFO/SCO	Project no.	PS00120016A

- Knee angle is measured with a special sensor based on magnetic principles.

[figure not shown]

Figure 3: Microprocessor controlled knee joint unit

The control paradigm is mainly based on the evaluation of motion signals. Thus, it can provide optimum support in every phase of the gait cycle. In level walking, the system would behave in the different gait phases according to the following table:

Gait phase	Knee joint resistance	Effect on gait.
Heel strike	High flexion Low extension	Stance phase stability, stance phase flexion is possible
Mid stance (rollover)	High flexion Controlled extension	Stance phase stability Stance phase extension controlled for soft extension stop and improved propulsion
Toe off	Low flexion Low extension	Swing initiation, knee can bend Extension is free.
Swing phase flex-	Controlled flexion Low extension	Knee flexion angle can be controlled to achieve a physiological knee angle

ottobock.	CLINICAL INVESTIGATION PLAN	Document number:	PD-PS00120016A-001
		Version number:	7
Project name	Clinical trial comparing C-Brace to KAFO/SCO	Project no.	PS00120016A

ion		Extension is free.
Swing phase extension	High flexion Low extension	Flexion resistance is high to provide support in case of stumbling. Extension is free.
Terminal swing	High flexion Controlled extension	Flexion resistance is high to provide support in case of stumbling. Extension is controlled for soft extension stop.

Table 1: Description of the knee joint resistance depending on the gait phase and the respective effect on gait.

The system only activates swing initiation at toe off if a signal pattern that is typical for level walking is detected.

The control system is kept as simple as possible; it is principally based on posture control. This method has proven to be appropriate for the control of prosthetic knee joints (e.g. C-Leg 4). For safety reasons also load signals representing the knee moment are taken into account. Therefore, the knee joint does not switch to a low flexion resistance for swing initiation if a flexion moment is measured. Such “default stance” behavior of the system is inherently safe.

5.3 Necessary training and experience to use the investigational device (C-Brace)

5.3.1 Orthopedic technician

The orthopedic technician needs a C-Brace (C-Brace 2) certification.

5.3.2 Patient

The patient will be trained to put on C-Brace, to use the cockpit app and perform adjustments safe and routinely. Training will be performed by a certified CPO or physiotherapist.

Patient will be discharged with C-Brace only if he/she demonstrated that he/she was able to walk safely and is able to program the device. This will be assessed with a benchmark system within the adaption phase (see section 7.3.4).

ottobock.	CLINICAL INVESTIGATION PLAN	Document number:	PD-PS00120016A-001
		Version number:	7
Project name	Clinical trial comparing C-Brace to KAFO/SCO	Project no.	PS00120016A

5.4 Comparator Devices

The C-Brace will be compared with the standard SCOs or KAFOs, which have been prescribed in clinical routine to the patient. All CE registered SCOs or KAFOs are allowed.

5.5 Accommodation to the devices

During the phase of system setup, patients will receive appropriate accommodation support.

For details of accommodation support, please see section 7.3.4.

5.6 Specific medical or surgical procedure involved

Not applicable.

5.7 Receipt, distribution and usage

During screening, the site will test the patients regarding the ability to use C-Brace. During this testing procedure, the parameters will be documented and sent to Ottobock afterwards.

Final assembly of the patient-specific C-Brace orthosis will be performed either at Ottobock SE & Co. KGaA in Duderstadt, Germany or at the study site. In case, Ottobock is responsible for assembly, Ottobock will provide the study site with the assembled C-Brace orthoses. All orthoses will be labeled with a specific label "For clinical investigation only". Shipment of the final assembled orthosis is done by Ottobock Duderstadt. In case assembly is done at the study site, Ottobock Duderstadt will provide the study site with sufficient mpKnee joints. The mpKnee joints will be labeled "For clinical investigation only". Traceability of all investigational devices is ensured by maintaining a device accountability log.

If study patients decide not to keep C-Brace for up to 24months after finishing the study, C-Brace needs to be sent back to Ottobock Duderstadt.

6 Study objectives and hypotheses

6.1 Objectives

6.1.1 Primary objective

Primary Efficacy Endpoint

ottobock.	CLINICAL INVESTIGATION PLAN	Document number:	PD-PS00120016A-001
		Version number:	7
Project name	Clinical trial comparing C-Brace to KAFO/SCO	Project no.	PS00120016A

Improvement of static and dynamic balance by using C-Brace compared to KAFO/SCO.

6.1.2 Secondary objectives

- To evaluate the effect of the C-Brace compared to KAFO/SCO on gait, balance, plain level walking, walking during more challenging tasks and divided attention tasks during walking.
- To assess and compare the safe use of the C-Brace compared to KAFO/SCO in regard to falls: frequency of falls, severity of falls, fall-related injuries, fear of falling and related treatment efforts.
- Evaluation of patient`s confidence in performing various ambulatory activities without falling using C-Brace compared to KAFO/SCO.
- Assessment of quality of life and re-integration to normal living using C-Brace compared to KAFO/SCO.
- Assessment of disability and impact on productivity.
- Assessment of patient`s C-Brace satisfaction and usage habits compared to KAFO/SCO.
- Reduced probability of falling more than once by using C-Brace compared to KAFO / SCO

6.1.3 Endpoints

Assessments will be taken at baseline with the patient`s own orthotic device, after completing the first randomization phase and after completing the second randomization phase. Please refer to section 8 Outcome Measures.

6.2 Hypothesis

The primary hypothesis is that the microprocessor based C-Brace technology will help moderately active patients to improve balance compared to a non-microprocessor controlled KAFO/SCO.

As a consequence, the C-Brace should help reduce the risk of falling/falls in these patients and eventually make them more independent in their daily life activities including their job and improve their quality of life, which represents the secondary hypothesis of the study.

ottobock.	CLINICAL INVESTIGATION PLAN	Document number:	PD-PS00120016A-001
		Version number:	7
Project name	Clinical trial comparing C-Brace to KAFO/SCO	Project no.	PS00120016A

7 Study design

This is a prospective international multicenter randomized controlled cross-over open-labeled trial.

The study will have multiple sites in the United States, Germany, Netherlands and Austria. In total 56 patients will be recruited. Patients can be enrolled in a competitive manner without any allocation.

7.1 Experimental plan

After obtaining informed consent, patients will be screened. Patients fulfilling inclusion/exclusion criteria will be enrolled in the study. After screening, a first baseline assessment will be conducted. Within maximum 48 hours, a second set of baseline data will be collected. Afterwards the participants will be randomly assigned to be fitted either with C-Brace or maintain his/her KAFO/SCO. The randomization procedure will be concealed and assigned off-site. After fitting, an accommodation period follows that will last up to 14 days prior home use. The first follow-up data collection will occur after 3 months after the initial home use period. Afterwards, the patients will cross over to KAFO/SCO or C-Brace, respectively. The participants who were fitted with C-Brace will cross over to KAFO/SCO and vice versa. Another accommodation phase will be offered for both C-Brace and KAFO/SCO wearers to ensure that the patient can properly use both devices before the cross-over home use period. The second follow-up data collection will occur after 3-months of home use. At the end of the study, the patients can choose to keep C-Brace until reimbursement or return to their original KAFO/SCO.

7.2 Measures taken to minimize bias

The research center will delegate the role of assessor to one trained employee. The assessor will be responsible for evaluating functionality of participants in the performance-based tests in all phases of the study. During all performance tests, patients will be instructed to refrain from giving any comments. The certified prosthetist (CPO) and physical therapist cannot be blinded.

7.3 Study visits and procedures

7.3.1 Patient enrollment

This study will enroll up to 150 eligible patients. At least 56 subjects passing screening will be randomized. Dropouts shall be replaced, a dropout rate of 20% is assumed. Recruitment planning shall be done in accordance with the capabilities of the centers. Competitive recruitment shall be allowed. All means to increase recruitment shall be taken.

ottobock.	CLINICAL INVESTIGATION PLAN	Document number:	PD-PS00120016A-001
		Version number:	7
Project name	Clinical trial comparing C-Brace to KAFO/SCO	Project no.	PS00120016A

Treatment failures: C-Brace must be fitted according to Ottobock instructions. During study visits, the C-Brace fitting quality will be checked; poor fitting quality needs to be corrected and may be reported as adverse event (AE) or adverse device effect (ADE). For definitions, please refer to section 12.2.

Patients who do not comply with using the C-Brace at least 1-2 hours per day 5 days per week will be included in the intention to treat analysis only; however, they will be excluded from the per-protocol analysis.

Potential patients will be called by the participating sites and pre-screened for study eligibility. In addition, patients contacting the sites or visiting them on a routine basis can be also pre-screened.

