9.3.1 Inclusion criteria

- Patient has been tested with the Trial Tool (DTO) and demonstrated the potential to utilize the C-Brace successfully (see section benchmarks: independent donning/doffing of the orthosis, charging of the device, transfers sit to stand/stand to sit, standing in the orthosis with or without assisted device for a minimum of 2 minutes, safe over ground ambulation, ambulatory turns and to perform a swing phase).
- Patient has a BBS score < 45
- Lower limb functional impairment according to CE label wording
- Prior active and compliant use of unilateral or bilateral KAFO or SCO in the past 3 months prior to enrollment in the study
- Patient meets minimum physical requirements to be fitted with a C-Brace, such as muscle status, joint mobility, leg axis and proper control of the orthosis must be guaranteed.

ottobock.	CLINICAL INVESTIGATION PLAN	Document number:	PD-PS00120016A-001
		Version number:	7
Project name	Clinical trial comparing C-Brace to KAFO/SCO	Project no.	PS00120016A

- The User must fulfill the physical and mental requirements for perceiving optical/acoustic signals and/or mechanical vibrations
- The existing muscle strength of the hip extensors and flexors must permit the controlled swing-through of the limb (compensation using the hip is possible).
- Patient's commitment to use C-Brace 2 at least 1-2 hours per day 5 days per week-
- Patient is ≥ 18 years old
- Patient is willing and able to independently provide informed consent.
- Person is willing to comply with study procedures

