9.3.2 Exclusion criteria

- Patient who is not able to follow the entire study visits or is unwilling/unable to follow the instructions
- Patient was not able to use DTO
- Patient who is not using an orthosis at least 1 to 2 hours/ day for 5 days per week
- Patient with body weight > 125 kg (includes body weight and heaviest object (weight) carried)
- Patient with Orthoprosthesis
- Patient with flexion contracture in the knee and/or hip joint in excess of 10°
- Patient with uncontrolled moderate to severe spasticity (relative contraindication moderate spasticity)
- Leg length discrepancy in excess of 15 cm
- Patient with unstable neurological or cardiovascular/pulmonary disease, cancer
- Pregnancy
- Patient using a C-Brace
- Patient with known vertigo or with history of falls unrelated to orthosis use or unrelated to motor disability
- Patient who has never been fitted an orthosis before
- Patient is not able to answer the self-administered questionnaires independently; for patients with upper extremity impairment is it allowed to verbally answer the questions.
- Patient participating already in a clinical study during this study's duration
- Patient participated in earlier C-Brace studies

Additional determination of exclusion criteria for Austrian centers:

Pregnant and nursing women are NOT allowed to participate in this study.

Women of childbearing age are only allowed to participate in this study, if they have confirmed that they are not pregnant before the study (according to a pregnancy test). They will be asked to perform pregnancy tests once a month during the study. Female patients will be asked to inform the investi-

ottobock.	CLINICAL INVESTIGATION PLAN	Document number:	PD-PS00120016A-001
		Version number:	7
Project name	Clinical trial comparing C-Brace to KAFO/SCO	Project no.	PS00120016A

gator immediately, if they become pregnant during the study, or suspect that they are pregnant. Their participation in the study will be terminated under these circumstances.

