10.3 Planned statistical analysis

In general, the most suitable statistical analysis consistent with the form of data will be used and the underlying assumptions of the statistical method will be verified through appropriate pre-tests.

ottobock.	CLINICAL INVESTIGATION PLAN	Document number:	PD-PS00120016A-001
		Version number:	7
Project name	Clinical trial comparing C-Brace to KAFO/SCO	Project no.	PS00120016A

The analysis will be performed on the intention-to-treat (ITT) population and then on the per-protocol (PP) population. The ITT population is defined as all the patients randomized into their randomization group, regardless of the treatment received or their outcome in the study. The PP population is defined as all the patients in the ITT population without any major protocol deviations

For the outcomes measures being evaluated, three assessments are undertaken:

after base line measurements with original orthosis (first baseline measurement)

after first follow up measurement with the C-Brace or original orthosis

after second follow-up measurement with the C-Brace or original orthosis

Quantitative variables will be summarized using standard descriptive statistics (average, standard deviation, median, minimum and maximum, first and third quartile). Qualitative variables will be described using group sizes and frequencies. When relevant, 95%confidence intervals will be given.

Patient characteristics at enrolment will be presented and compared in each group to ensure the groups are initially comparable. The features of any patients lost to follow-up will be studied and influence the imputation strategy as described in 10.2.

Patient profile plots for the outcome measures in both treatment groups for all three assessments will be viewed, showing imputed values. Furthermore, the group means in each treatment group will be evaluated. Outcome measures will be visualized for the crossover periods in scatter plots of first follow up measurement against second follow-up measurement in both treatment groups i.e. period vs period plots.

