15.2 Deviations from Clinical Study Protocol

A clinical study protocol deviation is any instance of failure to follow, intentionally or unintentionally, the requirements of the clinical study protocol (ISO 14155:2020).

Ottobock is responsible for analyzing deviations, assessing their significance, and identifying any additional corrective and/or preventive actions (e.g. amend the clinical study protocol, conduct additional training, etc.). Repetitive or serious investigator compliance issues may require initiation of a corrective action plan with the investigator, and in some cases, necessitate suspending site enrollment until the problem is resolved or ultimately terminating the investigator's participation in the study.

Major clinical study protocol deviations represent non-adherence to one or more inclusion and/or exclusion criteria or are considered to affect the safety and well-being of the patient. Major clinical

ottobock.	CLINICAL INVESTIGATION PLAN	Document number:	PD-PS00120016A-001
		Version number:	7
Project name	Clinical trial comparing C-Brace to KAFO/SCO	Project no.	PS00120016A

study protocol deviations increase the risk, decrease the benefit and/or affect the participant's rights, safety, and/or the integrity of the resultant data. They also may result from evidence of willful or knowing misconduct on the part of the investigator, or from ignorance of established research, medical, and ethical principles.

Examples for major deviations:

- Patients enrolled prior to EC notification of approval or after expiration of approval
- Enrollment of a patient outside the inclusion/exclusion criteria
- Use of an unapproved or expired informed consent form
- Inadequate/improper informed consent procedures
- Inclusion of patients who have not provided written consent
- Failure to maintain adequate patient records or proper study documentation

It is the responsibility of the Investigator not to deviate from the protocol approved by the EC, except as necessary to avoid an immediate hazard to the participant.

Procedure:

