23.3 Appendix III: Example of the phone call protocol

PHONE CALL 1 (1 Month)

THIS PHONE CALL HAS TO BE DONE IN THE **END OF MONTH 1** AFTER ASSESSMENT OF READINESS!

- Please remind the patient about the **minimum time of use** (1-2 hours, 5 days per week) of the current orthosis.
- Ask the patient some questions about **adverse events (AE) and device deficiencies (DD)**.
- Remind the patient to call the investigator immediately in the case of malfunctions, falls or other limiting events.
- Remind the patient to **document any falls and near falls as well as unexpected behavior of the current orthosis in the patient diary** and to bring the diary at each visit.
- If you need more space for your documentation please use page 8-9.

Please specify the use of the current orthosis in day(s)/week and the hour(s)/day:

Which orthosis (es) have you been using? (Check all that apply)	 C-Brace	 KAFO
Time using the orthosis (es):	 day(s)/ week	 day(s)/ week
	 hour(s)/ day	 hour(s)/ day
Please specify, if the patient uses the current orthosis ≤ 1 hour/day or < 5 days a week: _____ _____ _____		

Did you have any health impairments in the past	 YES	 NO	If YES, number of events:	
--------------------------------------------------------	------------------------------	-----------------------------	---------------------------	----------------------

ottobock.	CLINICAL INVESTIGATION PLAN	Document number:	PD-PS00120016A-001
		Version number:	7
Project name	Clinical trial comparing C-Brace to KAFO/SCO	Project no.	PS00120016A

Did any falls require medical attention in the past month ?	 Yes  No	If YES: Number of events: _ _
Did any falls cause permanent injury in the past month ?	 Yes  No	If YES: Number of events: _ _
Did any falls result in missed work in the past month ?	 Yes  No	If YES: Number of events: _ _

Date of signature	Name	Signature
_ _ _ _ 2 0 _ _ D D M M Y Y Y Y

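### The only stated use-based per-protocol exclusion names C-Brace and has no KAFO/SCO counterpart, so the exploratory per-protocol results may favour C-Brace

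*Combined protocol and SAP*

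**What the plan says.** Section 7.3.1 keeps one group in the intention-to-treat analysis only: "Patients who do not comply with using the C-Brace at least 1-2 hours per day 5 days per week". Of these it says "they will be excluded from the per-protocol analysis". KAFO/SCO is not mentioned there, and no other section supplies the matching sentence.

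Section 10.3 gives the general definition: "The PP population is defined as all the patients in the ITT population without any major protocol deviations". It contains no use threshold. Section 15.2 explains the term: "Major clinical study protocol deviations represent non-adherence to one or more inclusion and/or exclusion criteria", or effects on safety, rights or the integrity of the data. Its list is introduced by "Examples for major deviations" and does not name under-use of either device.

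The same threshold appears twice among the eligibility criteria. Section 9.3.1 asks for "commitment to use C-Brace 2 at least 1-2 hours per day 5 days per week". Section 9.3.2 excludes a "Patient who is not using an orthosis at least 1 to 2 hours/ day for 5 days per week", which covers any orthosis. Section 9.3 ties these criteria to registration.

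Minimum use is nevertheless expected of both devices. The calls in 7.3.5 cover home use in both arms and include a reminder of the minimum use time. The example form in 23.3 has a C-Brace and a KAFO column and instructs: "Please specify, if the patient uses the current orthosis ≤ 1 hour/day or < 5 days a week".

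Under 10.3.2 (primary efficacy outcome) the confirmatory BBS analysis uses the intention-to-treat population, and per-protocol p-values are exploratory. The section on secondary outcome analysis applies both populations to all secondary outcomes and treats all inference on them as exploratory.

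**The concern.** Use in a home-use period is behaviour after randomisation, and it may depend on how well the device works for that patient. Section 3 makes this link for conventional devices: it reports that most patients do not find the modest gain in function worth regular daily use. If the same holds for C-Brace, patients who under-use it tend to have small C-Brace minus KAFO/SCO differences, and dropping them raises the per-protocol mean. Patients who under-use KAFO/SCO because it serves them badly would tend to have large differences, and no stated rule drops them.

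This is a crossover, so a dropped patient loses both periods. The mechanism is a change in which patients are analysed, not an imbalance between arms.

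At stake is how the supportive analyses are read. A per-protocol result that agrees with or exceeds the intention-to-treat result is commonly taken as reassurance, and here part of that agreement could come from the selection rule. The cut-off is also not a single value. A patient reporting exactly 1 hour on 5 days meets the lower end of the 1-2 hour range in 7.3.1 but is flagged by the form in 23.3.

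**Working it through.** **Plan figure.** The documents give no per-protocol figure and no under-use rate, so there is no stated result to reproduce. The size of 56 in 10.1.2 does reproduce (44.2386 / 0.8 = 55.3, rounded up to 56), but it does not enter this check.

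**Inputs from 10.1.1.** Mean paired BBS difference 6.6429; standard deviation of that difference 4.9085.

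**Assumptions.** The paired difference is normal. Use of each device is a latent normal variable, with correlation rC (C-Brace) or rK (KAFO/SCO) to the paired difference. The lowest fraction q of users counts as under-users, with q = 5%, 10% or 20% for each device. A dropped patient loses both periods.

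**Step 1: C-Brace-only rule against all randomised patients.** For a normal variable truncated from below,

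shift = rC × 4.9085 × φ(z_q) / (1 − q),

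where z_q is the q-quantile of the standard normal distribution and φ its density.

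| q | φ(z_q)/(1 − q) | shift, rC = 0.3 | shift, rC = 0.5 |
|---|---|---|---|
| 5% | 0.1031/0.95 = 0.1086 | 1.4726 × 0.1086 = 0.16 | 2.4543 × 0.1086 = 0.27 |
| 10% | 0.1755/0.90 = 0.1950 | 1.4726 × 0.1950 = 0.29 | 2.4543 × 0.1950 = 0.48 |
| 20% | 0.2800/0.80 = 0.3500 | 1.4726 × 0.3500 = 0.52 | 2.4543 × 0.3500 = 0.86 |

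A simulation of 2,000,000 patients gives the same shifts. Relative to 6.6429 the range is 0.16/6.6429 = 2% to 0.86/6.6429 = 13%. With rC = 0 the shift is zero. With rC = −0.3 and q = 10% the mean falls to 6.36.

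**Step 2: C-Brace-only rule against one rule for both devices.** This comparison isolates the asymmetry. Simulated means at q = 10%, all-randomised mean 6.64:

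| rC | rK | C-Brace-only rule | same rule for both | difference |
|---|---|---|---|---|
| 0 | 0 | 6.65 | 6.65 | 0.00 |
| 0.3 | 0 | 6.93 | 6.93 | 0.00 |
| 0.3 | −0.3 | 6.93 | 6.65 | +0.29 |
| 0.5 | −0.5 | 7.12 | 6.65 | +0.48 |
| 0 | −0.3 | 6.65 | 6.36 | +0.29 |
| 0.3 | 0.3 | 6.93 | 7.21 | −0.27 |

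The means of 6.65 differ from 6.64 only by simulation error, and the differences were taken before rounding. A negative rK means that low KAFO/SCO use goes with a large advantage of C-Brace.

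**Reading.** When low use marks poor benefit from each device to the same degree (rK = −rC), the symmetric rule brings the mean back to the all-randomised value. The whole shift in step 1 is then due to the asymmetry. When KAFO/SCO use is unrelated to the difference, the symmetric rule leaves the shift as it was. When low use of either device goes with a small difference, the symmetric rule lies further from 6.64.

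**The case against.** Four stronger conclusions are tempting, and the documents support none of them.

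- *The per-protocol difference is biased towards C-Brace.* The documents do not say why patients under-use a device, and 7.3.1 requires poor fitting to be corrected. The sign depends on correlations that nobody has reported.
- *KAFO/SCO under-users stay in the set.* No rule removes them, but 15.2 is broadly worded, its list is only illustrative, and the 9.3.2 criterion covers any orthosis. They could be removed as major deviations. This route is at best discretionary: 9.3 ties the criteria to registration, and the relevant example in 15.2 concerns enrolment. Exclusion would then be automatic for C-Brace and, for KAFO/SCO, left to the sponsor's assessment of deviations in an open-label trial.
- *The rule inflates the effect by 6% to 25%.* A reader might set 6.6429 for compliant users against an all-patient mean of (1 − f) × 6.6429 + f × d, where f is the under-use fraction and d their true difference. With f = 0.10 and d = 3 this is 6.28, an excess of 0.36 (6%). With f = 0.20 and d = 0 it is 5.31, an excess of 1.33 (25%). That gap arises with any compliance-based set, and a two-device rule removes the same C-Brace under-users. It does not measure the asymmetry.
- *Sections 7.3.1, 10.3 and 15.2 contradict each other.* Absence from a list of examples is not a contradiction, and the commitment to C-Brace use is itself an inclusion criterion. The sections are not aligned, which is a lesser fault.

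The reach is also limited. The plan contains no decision rule based on agreement between the two populations.

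What survives is the text of 7.3.1: one explicit exclusion, for one device, on a measure that the trial collects for both.

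**Conclusion.** The point holds as an asymmetry in a stated rule. Followed as written, 7.3.1 conditions the per-protocol set on post-randomisation use of C-Brace alone. This may favour C-Brace if low use marks poor benefit from it.

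On the assumptions above, the one-sided rule shifts the mean BBS difference by about +0.16 to +0.86 points relative to the all-randomised mean. The amount attributable to asymmetry equals this only if KAFO/SCO under-use mirrors C-Brace under-use. It can be zero or negative otherwise. Under-use rates and correlations are assumed throughout.

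The confirmatory BBS conclusion does not depend on this. The exploratory per-protocol results for BBS and every secondary outcome, falls included, do. The change is a cheap improvement, not a repair of the main analysis.

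**What to change.** Put one use rule in the per-protocol definition in 10.3: a patient is excluded if use of either study orthosis in its home-use period falls below a single stated cut-off. The sponsor should choose that cut-off to replace the 1-2 hour range and reconcile it with the flag on the form in 23.3.

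Use the same data source for both devices, namely the phone-call question at the ends of months 1 and 2. State which reports count and that the KAFO column includes SCO. A common source matters because the C-Brace total-time read-out in 23.1 has no described KAFO/SCO equivalent, and the step counter runs for only 14 days.

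Align 7.3.1 and 15.2 with the new definition, fix the wording before database lock, and report per-protocol exclusions by device and sequence.

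The cost is wording, with no new data collection. The downsides are a somewhat smaller per-protocol set, no coverage of month 3 by the calls, and leaving the objective C-Brace time log out of the rule. A symmetric rule also still selects on behaviour after randomisation; it removes the one-sidedness, not the selection.
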